2 STUDY SCHEDULE (A MORE DETAILED TABLE IS SHOWN IN APPENDIX 1)

ACTIVITIES	Screening	Period 1				Period 2				Final visit/ETV ¹	
		Single Dose				Multiple Dose					
		Visit	V1	V2	V3	V4	V5	V6	V7		
Day	Day -14/-2	Day -1	Day 1/3	Day 4/5	Day 8/9	Day 10/13	Day 14/17	Day 18	Day 18 ²		
Informed consent	x										
Demography	x										
Lifestyle	x										
Medical and surgical history	x										
Physical examination³	x									x	
Prior and concomitant medications	x	x	x	x	x	x	x	x	x		
Height	x										
Body Weight³	x									x	
Laboratory analysis⁴	x									x	
Virology	x										
Serum pregnancy test (women)	x										
Urine multi-drug kit test	x	x									
Blood pressure and heart rate⁵	x		x (Day 1: pre-dose, 2 hours post-dose)	x (Day 5: 96 hours after Day 1)	x (Day 8: pre-dose, 2 hours post-dose)	x (daily from Day 10 to Day 13: pre-dose)	x (Day 14: pre-dose, 2 hours post-dose)	x (Day 18: 96 hours after Day 14)		x	
Alcohol breath test		x									
Urine pregnancy test (women)		x								x	
ECG⁶	x									x	
Inclusion/exclusion criteria	x	x									
Subject eligibility	x	x									
Enrolment and randomisation		x									
Confinement		x	x	x	x	x	x	x			
Discharge									x		
Investigational product administration			x ⁷ (Day 1)		x ⁷	x ⁷	x ⁷ (Day 14)				
Blood sampling for PK analysis			x ⁸	x ⁸	x ⁹	x ¹⁰	x ⁸	x ⁸			
Standardized meals¹¹		x	x	x	x	x	x	x			
Adverse event monitoring¹²	x	x	x	x	x	x	x	x	x		

1. *Early termination visit (ETV)*
2. *Final visit on day 18*
3. *Physical examination, including body weight, at screening and final visit/ETV*
4. *Laboratory analyses at screening and final visit/ETV*
5. *At pre-dose (before blood sampling and within 30 min of investigational product administration), at 2 h (± 15 min) and 96 h (± 15 min) after day 1 single dose and after day 14 last multiple dose. At pre-dose (before blood sampling and within 30 min of investigational product administration), and 2 h (± 15 min) after the day 8 first multiple dose. At pre-dose (before blood sampling and within 30 min of investigational product administration) on day 10 to day 13.*
6. *At screening and final visit/ETV*
7. *On day 1 (Period 1) and once daily from day 8 to day 14 (Period 2), at 8:00 \pm 1 h*
8. *At pre-dose (0), 0.5, 1, 1.5, 2, 3, 4, 6, 8, 12, 16, 24, 36, 48, 72 and 96 h post-dose after the first single dose (day 1) and the last multiple dose (day 14);*
9. *At pre-dose (0) and 0.5, 1, 1.5, 2, 3, 4, 6, 8, 12, 16 and 24 h post-dose after the first multiple dose (day 8)*
10. *At pre-dose (0) on each day (day 10-13)*
11. *Day -1: standardized dinner;*
Day 1, Day 8, Day 14: standardized lunch at approximately 5 h post-dose, standardized dinner at approximately 13 h post-dose;
Day 2 to Day 5, Day 9 to Day 13, and Days 15 to 17: standardized breakfast (after PK sampling), lunch and dinner;
Day 6 and Day 7: standardized breakfast, lunch, and dinner;
Day 18: standardized breakfast (after PK sampling)
12. *Adverse events monitored starting at the screening visit, immediately after informed consent, up to the final visit/ETV*

CDISC	Clinical Data Interchange Standards Consortium
CHMP	Committee for Medicinal Products for Human Use
CI	Confidence Interval
Cl/F	Apparent total body clearance
C_{ave_ss}	Average drug concentration at steady state
C_{max}	Maximum drug concentration
C_{max_ss}	Maximum drug concentration at steady state
C_{mix_ss}	Trough drug concentration at steady state
CRF	Case Report Form
CRO	Contract Research Organisation
CS	Clinically Significant
CV	Coefficient of Variation
DF%	Peak-trough fluctuation over one dosing interval at steady-state
DBP	Diastolic Blood Pressure
EC	Ethics Committee
ECG	Electrocardiogram
EMA	European Medicines Agency
ETV	Early Termination Visit
FDA	Food and Drug Administration
FSFV	First Subject First Visit
GCP	Good Clinical Practice
GLP	Good Laboratory Practice
HBs Ag	Hepatitis B virus surface antigen
HCV Ab	Hepatitis C virus antibodies
HIV	Human Immunodeficiency Virus
HR	Heart Rate
ICH	International Conference on Harmonisation
IRB/IEC	Institutional Review Board/Independent Ethics Committee
IMP	Investigational Medicinal Product
IUD	Intra-Uterine Device
K_{el}	Terminal elimination rate constant
LLOQ	Lower Limit of Quantification
LQL	Lower Quantification Limit
LSLV	Last Subject Last Visit
MAO	Monoamino oxidase
MCH	Mean Cell Haemoglobin
MCHC	Mean Cell Haemoglobin Concentration

MCV	Mean Cell Volume
MedDRA	Medical Dictionary for Regulatory Activities
MRT	Mean residence time
MW	Molecular Weight
N	Normal
NA	Not Applicable
NC	Not calculated
NCS	Not clinically significant
OTC	Over The Counter
PD	Parkinson's disease
PK	Pharmacokinetics
PT	Preferred Term
PTAE	Pre-Treatment Adverse Event
R_{acc}	Accumulation ratio
RBC	Red Blood Cells
SAE	Serious Adverse Event
SBP	Systolic Blood Pressure
SD	Standard Deviation
SDTM	Study Data Tabulation Model
SmPC	Summary of Product Characteristics
SNRI	Serotonin–norepinephrine reuptake inhibitors
SOC	System Organ Class
SOP	Standard Operating Procedure
SSRI	Selective serotonin reuptake inhibitors
SUSAR	Suspected Unexpected Serious Adverse Reaction
T	Test
T1	Xadago® 50 mg
T2	Xadago® 50 mg
TEAE	Treatment-Emergent Adverse Event
THC	Delta-9-tetrahydrocannabinol
$t_{1/2}$	Apparent terminal elimination half-life
t_{max}	Time to achieve C_{max}
V_d/F	Apparent volume of distribution associated with the terminal slope
WBC	White Blood Cells
WHO	World Health Organisation
WHODDE	World Health Organisation Drug Dictionary Enhanced

4 INTRODUCTION

4.1 Safinamide

4.1.1 *Background*

The α -aminoamide derivative safinamide [(S)-(+)-2-[4-(3-fluorobenzyloxy) benzylamino] propanamide], developed as methane sulfonate salt, is an original anticonvulsant and antiparkinson agent which has been granted marketing authorisation in 9 EU Member States (i.e. Germany, Italy, Spain, Portugal, United Kingdom, Belgium, The Netherlands, Sweden and Denmark), in Norway and in Switzerland under the brand name of Xadago[®], 50 and 100 mg, film-coated tablets (2), for the treatment of adult patients with idiopathic Parkinson's disease (PD) as add-on therapy to a stable dose of Levodopa (L-dopa) alone or in combination with other PD medicinal product in mid-to late-stage fluctuating patients (3).

Safinamide uniquely combines potent, selective and reversible inhibition of monoamino oxidase B (MAO-B) with blockade of voltage-dependant Na^+ and Ca^{2+} channels and inhibition of glutamate release (4,8), thus showing a novel mode of action, targeting both dopaminergic and glutaminergic systems (9,10).

Data from Phase III clinical studies gave evidence that safinamide 50 or 100 mg/day improves the motor function in Parkinson's disease when prescribed as add-on therapy to dopamine agonists or L-dopa (3).

4.1.2 *Clinical pharmacology and pharmacokinetics*

Safinamide pharmacokinetics after single and multiple dose administrations have been described (11,12). At single ascending oral doses ranging from 2.5 to 10.0 mg/kg, safinamide was absorbed in a linear and dose-proportional fashion. Peak plasma levels were obtained on average at 1.8 to 2.8 h post-dose. Concentrations declined with a terminal half-life of 20 - 23h (11,12). Absolute bioavailability is high (95%), showing that safinamide is almost completely absorbed after oral administration and first pass metabolism is negligible (SmPC, 3). A complete long-lasting inhibition of platelet MAO-B activity was observed at all doses tested. Food intake prolonged the rate but did not affect the extent of safinamide absorption (11,12). Studies in healthy volunteers (13,15) demonstrated that safinamide does not affect oral tyramine metabolism mostly mediated by the intestinal MAO-A, and confirm that it can be administered without tyramine-related dietary restrictions.

4.1.3 *Safety*

The overall safety profile of Xadago[®] is based on the clinical development program performed on over 3000 subjects, of which over 600 were treated for more than 2 years.

The most common side effects related to safinamide are dyskinesia, somnolence, dizziness, headache, insomnia, nausea and orthostatic hypotension. Serious adverse reactions, such as hypertensive crisis (high blood pressure, collapse), neuroleptic malignant syndrome (confusion, sweating, muscle rigidity, hyperthermia, CPK increase), serotonin syndrome (confusion, hypertension, muscle stiffness, hallucinations), and hypotension, are known to occur with the concomitant use of SSRIs, SNRIs, tricyclic/tetracyclic antidepressants and MAO inhibitors.

With MAO-inhibitors there have been reports of drug interactions with concomitant use of sympathomimetic medicinal products. Impulse control disorders, pathological gambling, increased libido, hypersexuality, compulsive spending or buying, binge eating and compulsive eating can occur in patients treated with dopamine agonists and/or other dopaminergic treatments.

A complete list of adverse reactions observed with safinamide is presented in the SmPC (3).

4.2 Study rationale

The present study will be part of safinamide registration package in China and was designed according to CFDA guideline recommendations (1).

Safinamide has been granted marketing authorization in EU (2015), US (2017) and Switzerland (2015).

In the present study, safinamide pharmacokinetic profile, safety and tolerability after single dose and at steady state will be investigated for the first time in Chinese healthy male and female volunteers.

4.3 Risks and benefits

For AEs occurred with safinamide in previous clinical studies, please refer to § 4.1.3 and the SmPC (3). The most common side effects are dyskinesia, somnolence, dizziness, headache, insomnia, nausea and orthostatic hypotension.

Based on the clinical experience, no particular risks are expected for the study subjects considering safinamide 50 mg and 100 mg multiple dose administrations.

5 STUDY OBJECTIVES

The objective of the study is to evaluate safinamide pharmacokinetic profile, safety and tolerability after single and multiple dose administration to healthy adult Chinese volunteers

5.1 Primary end-point

- To evaluate plasma safinamide pharmacokinetic parameters after single and multiple dose administration of the investigational products.

5.2 Secondary end-point

- To collect safety and tolerability data after single and multiple dose administration of the investigational products.

6 CLINICAL SUPPLIES

6.1 Treatment

6.1.1 *Description of investigational products*

TEST PRODUCT 1 (T1)

Name	Xadago® 50 mg film-coated tablets
Active ingredient	Safinamide methanesulphonate (corresponding to 50 mg safinamide)
Marketing Authorization Holder	Zambon S.p.A., Italy
Pharmaceutical form	Film-coated tablets
Dose	Single 50 mg dose on day 1 Multiple 50 mg doses, once daily, for 7 days
Administration route	Oral

TEST PRODUCT 2 (T2)

Name	Xadago® 100 mg film-coated tablets
Active ingredient	Safinamide methanesulphonate (corresponding to 100 mg safinamide)
Marketing Authorization Holder	Zambon S.p.A., Italy
Pharmaceutical form	Film-coated tablets
Dose	Single 100 mg dose on day 1 Multiple 100 mg doses, once daily, for 7 days
Administration route	Oral

6.1.2 *Dose regimen*

Subjects will be randomised to two study cohorts to receive single and multiple doses of 50 mg safinamide (cohort 1), or single and multiple doses of 100 mg safinamide (cohort 2), according to the study randomised, parallel-group design, as follows:

- Cohort 1: One (1) safinamide 50 mg film-coated tablet will be administered on day 1 followed by 7 safinamide 50 mg film-coated tablets in total from day 8 to day 14 and hence administered 1 tablet o.d. from day 8 to day 14.
- Cohort 2: One (1) safinamide 100 mg film-coated tablet will be administered on day 1 followed by 7 safinamide 100 mg film-coated tablets in total from day 8 to day 14 and hence administered 1 tablet o.d. from day 8 to day 14.

Dose regimens are also summarised in the scheme below:

Table 6.1.2.1 Study dose regimen

Cohort	Period 1 - single dose	Washout	Period 2 - Multiple doses
	Day 1		Days 8 - 14
Cohort 1	50 mg po	7 days	50 mg po o.d for 7 days
Cohort 2	100 mg po		100 mg po o.d. for 7 days

6.1.3 *Route and method of administration*

The investigational products will be orally administered in the morning, at 8:00±1h, under fasting conditions, with 240 mL (total volume) of still mineral water.

A mouth-and-hand check will be performed immediately after dosing to ensure treatment compliance.

6.1.4 *Investigational product distribution*

All doses of the investigational products will be administered at the clinical centre by the investigator or by his/her deputy. The investigational products will be exclusively used for the present clinical study and will only be administered to the subjects enrolled in the study.

6.2 *Packaging and labelling*

Packaging and labelling for the clinical study will be performed by a GMP compliant vendor, delegated by Zambon S.p.A., Italy.

Subjects' kit labelling will report all the information according to the Annex 13 to the Good Manufacturing Practice (published by the Commission in The rules governing medicinal products in the European Community, Volume 4, 16), as follows:

- a. Name, address and telephone number of the sponsor, contract research organisation or investigator (the main contact for information on the product, clinical study)
- b. Pharmaceutical dosage form, route of administration, quantity of dosage units, and the name/identifier and strength/potency
- c. The batch and/or code number to identify the contents and packaging operation
- d. A study reference code allowing identification of the study, site, investigator and sponsor if not given elsewhere
- e. A blank space for subject enrolment Nr. (to be reported by hand by the Investigator) and where relevant, the visit number
- f. The name of the investigator (if not included in (a) or (d))
- g. Directions for use (reference may be made to a leaflet or other explanatory document intended for the study subject or person administering the product)
- h. “For clinical study use only” or similar wording

- i. The storage conditions
- j. Period of use (use-by date, expiry date or re-test date as applicable), in month/year format and in a manner that avoids any ambiguity
- k. “Keep out of reach of children”

The label will be in Chinese language.

6.3 Storage conditions

The investigational products will be stored at $\leq 25^{\circ}\text{C}$ in a dry locked place, sheltered from light.

6.4 Drug accountability

The vendor delegated by Zambon S.p.A., Italy, will provide the clinical centre with a sufficient number of individual subject kits to conduct the study, plus sufficient reserve kits.

After receipt of the drug supply, the Pharmacist will confirm in writing by signing and dating standard drug accountability forms. At the end of the study, the drug product will be maintained in the original containers.

At the end of the study, used, unused and partially used supplies of the investigational products, provided by the vendor delegated by Zambon S.p.A., Italy, will be stored as detailed in § 6.3 above and then disposed of (upon sponsor written authorisation), after assessment of drug accountability.

7 INVESTIGATIONAL PLAN

7.1 Overall study design

Phase I, single centre, single and multiple-dose, open-label, randomised, parallel-group, pharmacokinetics, safety and tolerability clinical study.

7.2 Discussion of design

Following a specific request of CFDA, the present study will be part of safinamide registration package in China and was designed according to CFDA guideline recommendations (1).

Safinamide has recently been granted marketing authorization in EU, Norway and Switzerland on the basis of the results of clinical trials performed in European countries. In the present study, safinamide pharmacokinetic profile, safety and tolerability after single dose and at steady state will be investigated for the first time in Chinese healthy male and female volunteers.

Two single doses (i.e. 50 and 100 mg) of safinamide will be administered to two subject¹ cohorts. The study will continue with multiple administrations of safinamide 50 and 100 mg, orally taken once a day for 7 days.

The 50 and 100 mg oral doses have been selected according to the common clinical practice (see Xadago[®] SmPC). These doses were investigated in the previously performed Phase III clinical trials. The volunteers will be assigned to the two cohorts according to the study randomised, parallel-group design.

Safinamide pharmacokinetic profile will be investigated after single dose, according to CFDA guidance requirements, and at steady state since multiple doses are administered in the clinical practice. Safinamide steady state should be reached after 5 or 6 days of treatment (day 13-14 in this study). Safinamide pre-dose concentrations will be assessed before the last 5 doses (days 10-14).

An open design was chosen. However, no bias on study outcome is expected considering that the study PK endpoints are based on the objective measurement of safinamide in plasma. Blood sampling time-points were selected on the basis of the known PK profile of safinamide. The sampling time lasts for about 4-7 elimination half-lives (mean PK half-life: 20-23 h) after both single dose and the last multiple dose administration.

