10.3 Sampling for pharmacokinetic analysis

10.3.1 *Venous blood sampling*

Venous blood samples (up to 10 mL) will be collected from a forearm vein at the following times:

- At pre-dose (0 h), 0.5, 1, 1.5, 2, 3, 4, 6, 8, 12, 16, 24, 36, 48, 72 and 96 h post-dose after the first single dose (days 1-5) and the last multiple dose (days 14-18)
- At pre-dose on days 10-13
- At pre-dose (0 h) and 0.5, 1, 1.5, 2, 3, 4, 6, 8, 12, 16 and 24 h post-dose after the first multiple dose (days 8-9)

Actual sampling times for each subject will be recorded in the individual CRFs. The actual sampling times should not exceed the recommended tolerance ranges presented in the following table. Any deviation outside the recommended ranges will be verified through Data Clarification Forms and, if confirmed, will be reported as protocol deviation, although it will not automatically lead to the exclusion of the concerned subjects from the PK set.

Table 10.3.1.1 Tolerance ranges for the scheduled sampling times

Sampling time	Tolerance range
Pre-dose (0)	Within 30 minutes before investigational product administration
0.5 h (30 min)	± 1 min
1, 1.5 h	± 3 min
2, 3, 4 h	± 5 min
6, 8, 12, 16, 24 h	± 10 min
36, 48 h	± 30 min
72, 96 h	± 60 min

Blood samples for PK analysis will be collected using an indwelling catheter with switch valve. The cannula will be rinsed, after each sampling, with about 1 mL of sterile saline solution. The first 2 mL of blood will be discarded at each collection time.

The remaining 6 mL will be collected from the catheter into blood collection tube (Li-heparin). Samples handling and processing is described in study specific lab manual.

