12.2 Pharmacokinetic assessments

12.2.1 Pharmacokinetic parameters

The following safinamide PK parameters will be measured and/or calculated with a Non-Compartmental Analysis (NCA) using Phoenix WinNonlin v6.3 (or higher).

After single dose and first multiple dose (day 1 and day 8):

- C_{max} : Maximum safinamide plasma concentration
- t_{max} : Time to achieve C_{max}
- AUC_{0-t} : Area under the concentration-time curve from single dose administration to the last quantifiable concentration time t
- AUC_{0-24h} : Area under the concentration-time curve in the tau interval (from single dose administration to 24 h post dose)

After single dose (day 1):

- K_{el} : Apparent terminal elimination rate constant, calculated, if feasible, from the slope of a log-linear regression using at least 3 last concentration $>$ LLOQ points
- $t_{1/2}$: Apparent terminal elimination half-life, calculated, if feasible, as $\ln 2/K_{el}$
- $AUC_{0-\infty}$: Area under the concentration-time curve extrapolated to infinity, calculated, if feasible, as $AUC_{0-t} + C_t/\lambda_z$, where C_t is the last measurable drug concentration
- V_d/F : Apparent volume of distribution associated with the terminal slope, calculated, if feasible, as $Dose/(AUC_{0-\infty} * K_{el})$

Cl/F:	Apparent total body clearance, calculated, if feasible, as Dose/AUC _{0-∞}
MRT:	Mean residence time, calculated, if feasible, as AUMC _{0-∞} /AUC _{0-∞} , were AUMC _{0-∞} is area under the moment concentration-time curve extrapolated to infinity

The sampling schedule is considered adequate if the ratio AUC_{0-t}/AUC_{0-∞} equals or exceeds a factor of 0.8 (i.e. if %AUC_{extra} is <20%) for more than 80% of the individual PK profiles. This assures that AUC_{0-t} covers a sufficient percentage of the theoretical total extent of exposure.

The quality of log-linear regression (and, consequently, the reliability of the extrapolated PK parameters) should be demonstrated by a determination coefficient $R^2 \geq 0.8$. Individual extrapolated parameters, when considered unreliable, will be reported as NC (not calculated).

After multiple dose (day 14):

C _{max_ss} :	Maximum safinamide plasma concentration at steady state
t _{max_ss} :	Time to achieve C _{max_ss}
AUC _{0-t,ss} :	Area under the concentration-time curve at steady state from the last dose administration to the last quantifiable concentration time t

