3.2.2 Pharmacokinetic Variables

Unless otherwise stated, derivation of Pharmacokinetic (PK) parameters will be the responsibility of Qualitative Clinical Development (QCD), PAREXEL International. The following PK parameters will be determined for Investigational Medicinal Product (IMP) in plasma following single dose and multiple dose administration:

Table 1 Pharmacokinetic Parameters after Single Dose Administration

| Parameter | Definition |
|--------------------|---|
| C_{\max} [1] | Maximum observed concentration |
| t_{\max} [1] | Time corresponding to occurrence of C_{\max} |
| $t_{1/2}$ | Apparent terminal elimination half life |
| C_{last}/C_t | Last quantifiable concentration |
| AUMC | Area under the first moment of the concentration-time curve |
| K_{el} | Terminal elimination rate constant |
| $AUC_{(0-t)}$ [1] | AUC from time zero to the last quantifiable concentration |
| $AUC_{(0-24)}$ [1] | AUC over the dosing interval (24 hours) |
| $AUC_{(0-\infty)}$ | AUC from time zero extrapolated to infinity |
| % AUC_{ex} | Percentage of $AUC_{(0-\infty)}$ obtained by extrapolation |
| MRT | AUMC/AUC |
| CL/F | Apparent clearance following oral administration |
| V_d/F | Apparent volume of distribution during terminal phase |

[1] These parameters will also be calculated after first multiple dose (day 8).

Table 2 Pharmacokinetic Parameters after Multiple Dose Administration

| Parameter | Definition |
|---------------------|---|
| $C_{\max,ss}$ | Maximum observed concentration at steady state |
| $C_{\min,ss}$ | Minimum observed concentration at steady state |
| $t_{\max,ss}$ | Time corresponding to occurrence of $C_{\max,ss}$ at steady state |
| $K_{el,ss}$ | Terminal elimination rate constant at steady state |
| $AUC_{(0-t),ss}$ | AUC to last observed concentration at steady state |
| $AUC_{(0-\tau),ss}$ | AUC over the dosing interval at steady state |
| CL/F_{ss} | Apparent clearance following oral administration at steady state |
| V_d/F_{ss} | Apparent volume of distribution during terminal phase at steady state |
| $C_{ave,ss}$ | Average concentration at steady-state |
| DF% | Peak trough fluctuation |
| $R_{acc,AUC}$ | Accumulation ratio, based on AUC |
| $R_{acc,C_{\max}}$ | Accumulation ratio, based on C_{\max} |

Pharmacokinetic Parameter Calculation Methods

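### Does sampling to 96 h cover too few half-lives for mean residence time, and does the SAP leave that parameter undefined?

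*Protocol*

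**What the plan says.** Protocol Final 3.0, section 7.2, explains the sampling length: "The sampling time lasts for about 4-7 elimination half-lives (mean PK half-life: 20-23 h". It applies this to the single dose and to the last multiple dose alike. Section 4.1.2 gives the same half-life: "Concentrations declined with a terminal half-life of 20 - 23h (11,12". In section 10.3.1 both full profiles end at 96 h: "24, 36, 48, 72 and 96 h post-dose after the first single dose (days 1-5) and the last multiple dose (days 14-18".

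MRT is one of six parameters derived after the day-1 dose only (section 12.1.1). Section 12.2.1 defines it, where feasible, as AUMC0-∞ divided by AUC0-∞, and says of AUMC0-∞ that it "is area under the moment concentration-time curve extrapolated to infinity". Three safeguards stand in the same section:

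- The adequacy rule that begins "The sampling schedule is considered adequate if the ratio" requires AUC0-t/AUC0-∞ of at least 0.8 in more than 80% of profiles.
- The terminal regression should reach R² of at least 0.8.
- Extrapolated values judged unreliable are reported as not calculated.

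SAP 2.0, section 3.2.2, Table 1, describes AUMC as "Area under the first moment of the concentration-time curve" and MRT as AUMC over AUC. Neither row has time limits, although the table lists AUC to the last quantifiable time, to 24 h and to infinity. The calculation list below it covers %AUCex, CL/F and Vd/F but has no line for AUMC or MRT. The SAP abbreviation list has MRT extrapolated to infinity (and its steady-state counterpart) and no truncated MRT.

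**The concern.** Two things look wrong together. The coverage claimed in 7.2 reaches 7 half-lives, and the schedule delivers fewer than 5. For AUC the difference hardly matters, but the first moment weights late concentrations by time, so its tail is several times heavier. The adequacy rule tests AUC only, so it would not reveal a heavy AUMC tail.

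In addition, a programmer who works from Table 1 alone could take AUMC and AUC to the last sample. MRT would then be 12-17% below the protocol's quantity. Against the precision of a cohort mean that is not small. If the between-subject CV of MRT is 20-30% (an assumption; the documents give none), the standard error with 12 subjects is 20/√12 = 5.8% to 30/√12 = 8.7%. MRT is listed among the primary variables, so a wrong value would reach the main results table.

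**Working it through.** **Inputs.** Last sample 96 h (protocol 10.3.1). Mean half-life 20-23 h (4.1.2 and 7.2). Time of peak for the oral model: "Peak plasma levels were obtained on average at 1.8 to 2.8 h post-dose" (4.1.2).

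**Coverage.** 96/20 = 4.80 and 96/23 = 4.17. With the ±60 min window at 96 h the range is 95/23 = 4.13 to 97/20 = 4.85. The 4 reproduces and the 7 does not. Seven half-lives would need sampling to 7 × 20 = 140 h up to 7 × 23 = 161 h, or a half-life of 96/7 = 13.7 h. The day-8 pre-dose sample, 168 h after the single dose, gives 168/23 = 7.3 to 168/20 = 8.4. It is not part of the day-1 profile and has no counterpart after day 14.

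**Extrapolated share.** For a mono-exponential decline let x = ln 2 × 96 / half-life. Then:

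- share of AUC beyond 96 h = e^(−x)
- share of AUMC beyond 96 h = e^(−x) × (1 + x)
- MRT0-t / MRT0-∞ = (1 − AUMC share) / (1 − AUC share)

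At 20 h: x = 3.327; e^(−x) = 0.0359; 0.0359 × 4.327 = 0.155; ratio = 0.845/0.964 = 0.876.

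| Case | x | AUC beyond | AUMC beyond | MRT ratio |
|---|---|---|---|---|
| half-life 20 h | 3.327 | 3.6% | 15.5% | 0.876 |
| half-life 23 h | 2.893 | 5.5% | 21.6% | 0.830 |
| exactly 7 half-lives | 4.852 | 0.8% | 4.6% | 0.962 |
| exactly 4 half-lives | 2.773 | 6.3% | 23.6% | 0.815 |

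The last row matters. The lower end of the protocol's own range implies a heavier AUMC tail than the schedule delivers.

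**Check with an absorption phase.** A one-compartment oral model with tmax 1.8-2.8 h, the planned sampling times and linear-up/log-down trapezoids gives AUC extrapolation of 3.6-5.7% and AUMC extrapolation of 15.5-21.6%. MRT0-∞ is 29.3-33.9 h and MRT0-t is 25.7-28.2 h, with ratios of 0.88-0.83.

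**How fragile is MRT to infinity?** In the same model, an elimination rate 10% too high lowers MRT0-∞ by 1.4-1.9%, and one 10% too low raises it by 1.8-2.4%. The corresponding changes in AUC0-∞ are −0.3 to −0.5% and +0.4 to +0.6%. A large extrapolated share is therefore not a large error.

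**Which MRT does the plan mean?** The protocol synopsis and section 12.2.1 both give zero to infinity for numerator and denominator. The SAP abbreviation list agrees. Table 1 omits the limits but does not contradict them. Section 1 of the SAP describes the document as adding details that the protocol does not give, and this one the protocol gives.

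**The case for a change.** The strongest case for a change is that the AUC rule can pass a profile whose MRT is mostly extrapolated. AUC extrapolation reaches 20% only when x = ln 5 = 1.609, a half-life of 41 h, where the AUMC share is 0.2 × 2.609 = 52%. AUMC extrapolation passes 20% already at a half-life of 22.2 h, where AUC extrapolation is 5%. R² does not fill this gap: perfectly log-linear data have R² = 1 and the same tail. The SAP also lets the PK scientist use fits below 0.80. Writing the limits into Table 1, correcting 7.2 and adding a column for the extrapolated share of AUMC would cost a few lines.

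All of this arithmetic stands. It does not lead to a different result:

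- **Protocol 7.2.** Replacing the 7 alters no sample, parameter or decision. The documents call 20-23 h a mean, so a spread of individual half-lives may lie behind the range. None is given, so the 7 is unsupported rather than shown to be wrong.
- **SAP limits.** The 12-17% bias needs a programmer to depart from an explicit protocol definition. An analyst deriving MRT would take it from there.
- **A 20% limit on AUMC.** The documents set 20% for AUC only. Carried over to AUMC it would flag about 15-63% of subjects, if half-life has a median of 20-23 h and a CV of 10-30% (assumption). It would separate good profiles from poor ones badly.
- **Visibility.** Table 1 includes the last concentration, Kel and AUMC, and sections 4.10.1 and 4.10.2 list concentrations and parameters by subject. If AUMC is taken to infinity, its extrapolated part, t × Ct/Kel + Ct/Kel², can be rebuilt from the listings to within the sampling window.

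**Conclusion.** The concern does not call for a change. The upper figure in 7.2 is a slip, or an unsourced range, in background rationale. The true coverage of 4.2-4.8 half-lives lies inside the range stated. The missing limits in SAP Table 1 are a gap that the protocol's own definition fills. If that definition is followed, the 12-17% shift does not arise, and the remaining sensitivity is about 2% of MRT for a 10% error in the elimination rate. MRT is one of 4 + 6 + 10 = 20 parameters named in section 12.1.1, all summarised descriptively, and the protocol tests no hypothesis.

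This rests on a mono-exponential decline at the stated mean half-life, on all samples to 96 h being quantifiable (no LLOQ is given), and on MRT being programmed to infinity. Subjects with half-lives above 23 h would have more than 21.6% of AUMC extrapolated. The rule on reporting unreliable extrapolated values as not calculated applies to them.
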